Post-treatment assessment: Participants will return for questionnaire completion and movement pattern assessment immediately after treatment. We will compare pre-treatment measures to post-treatment measures of both treatment groups to assess change in functional ability (HOOS) and movement patterns. Additionally, participants will complete a questionnaire developed to determine barriers to treatment adherence and to assess 1) treatment receipt, '*did the participant receive the treatment as intended*' and 2) treatment enactment, '*was the participant able to successfully implement their new skills*'.^{7, 8} To assess sustained effects of treatment, participants enrolled at the Washington University site will return for questionnaire completion and laboratory testing 1-2 years after treatment

Additional measures: We will collect additional measures, to assist in the future trial development. To assess the feasibility of using PROMIS, the NIH-funded Patient-Reported Outcomes Measurement Information System for people with PAHD, we will use the computer-adapted version of the physical function and mobility domains. Using previously reported methods,²³ we will assess hip muscle strength pre- and post-treatment. Finally, using additional funding from Washington University (See letter, [name]), participants will complete study questionnaires, electronically administered, 6 and 12 months after treatment to assess durability of post-treatment improvement.

Sample size considerations: With a sample size of 46 (23/group), the 95% confidence bounds (CBs) around our overall rates of adherence and retention will be between 78% and 96%, meaning that estimates will be within 9% of the true rate. The within site and within group estimates of adherence will be within 13% of the true rate. These calculations assume that the observed rates will be at least 90%, which is reasonable to expect based on our preliminary data. Aim 2 will estimate intervention effect sizes and as such, the study is not designed to generate definitive results. However, with at least 20 participants/group completing pre- and post-testing, the study will have 80% power to detect large effect sizes of 0.9 or above, with 95% CBs between 0.27 and 1.53. We note that preliminary data for the primary outcomes indicate that approximately 50% of the variance in change is explained by the pre-treatment value, and thus power and precision will be increased by including this covariate in the analyses.

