We anticipate no problems enrolling sufficient participants for this feasibility study. We were able to enroll 3-5 participants per month during our previous study. To improve our likelihood of meeting recruitment goals, we have added the University of Pittsburgh site and established collaborations with additional healthcare providers in St. Louis. We have also removed the restriction from the previous study for body mass index (previously <30 kg/m² required for kinematic testing). Support from the Data Coordination Center ([name], Director) will assist in optimizing retention rate and patient follow-up. Additionally, we will provide compensation of \$25/hour to offset travel effort and costs related to the testing sessions and treatment will be provided at no charge.

Statistical Analysis: The primary data analyses for Aim 1 will be descriptive, and include reporting the rate of recruitment, screening, and enrollment for all potential participants considered for the study; and reasons for non-enrollment. Adherence, retention, and fidelity rates will be categorized using the specified thresholds and reported with 95% CBs. Uncategorized rates will be compared between sites and groups by Wilcoxon's test. Aim 2 will generate estimates of effect sizes. We will report change between pre-and post-treatment with 95% CBs. Inferential analyses will compare the change in response to treatment using analysis of covariance (ANCOVA) where change is the dependent variable and the pre-treatment value is the covariate. Accounting for variation in pre-treatment function will increase the precision of the between-group comparisons and also adjust the treatment effect estimates for possible imbalances between groups. If statistical assumptions are not satisfied, transformations will be explored or nonparametric covariance analyses³⁵ will be used.

Data Management and Quality Control: Study data will be electronically captured using the REDCap system hosted in a limited access data center managed by the Data Coordinating Center. Additional quality control programs will verify that study identification numbers are accurately labeled, evaluate consistency over time, and check for incomplete or overdue data. Routine reporting will monitor recruitment and retention, overall quality, and protocol deviations. Throughout the study, standardization of procedures across sites will be ensured by dynamic training and monitoring that includes site visits and remote auditing.

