Significance and future directions: Information from the current study regarding the participants' ability to adhere to treatment, the treatment providers' ability to adhere to the treatment protocol and effect size estimates will guide the future, large RCT. Should the feasibility study indicate that modifications are needed, these will be made prior to the large RCT. Feedback from study participants and the treatment providers will be used to improve participants adherence and treatment fidelity. The future RCT will include assessment of patient-reported function and movement patterns from the proposed study and bony abnormalities. A better understanding of the association among these factors and treatment prognosis will help us develop improved treatment strategies and to better match treatment to patients.

Intra-articular, prearthritic hip disorders result in significant limitations in the young adult and are likely precursors to osteoarthritis. MPT is an innovative treatment approach with the potential to optimize treatment outcomes, nonsurgical and surgical, for people with PAHD. Further, MPT may provide a strategy for injury prevention, particularly those injuries of insidious nature. Ultimately this work will lead to better overall outcomes, reduced healthcare cost and reduced patient burden.

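### Do the Aim 2 power and confidence bounds need restating because they ignore the baseline covariate in the planned ANCOVA?

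*Combined protocol and SAP*

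**What the plan says.** Sample size considerations opens its precision statement for Aim 1 with "With a sample size of 46 (23/group" and then turns to Aim 2. It describes Aim 2 as estimating effect sizes and says that the study is not meant to be definitive. Assuming that 20 or more people in each arm have both assessments, it then claims: "the study will have 80% power to detect large effect sizes of 0.9 or above, with 95% CBs between 0.27 and 1.53". The following sentence reports from preliminary data that "approximately 50% of the variance in change is explained by the pre-treatment value", and concludes that power and precision will rise once this covariate is included.

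Statistical Analysis sets the between-group comparison as "analysis of covariance (ANCOVA) where change is the dependent variable and the pre-treatment value is the covariate", and repeats that adjustment will sharpen the comparison. Significance and future directions says that, together with information on participant and provider adherence, "effect size estimates will guide the future, large RCT".

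The plan gives no adjusted detectable effect or adjusted bounds. It does not say which SD standardises the effect size.

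**The concern.** Aim 2 is there to deliver an effect size and its precision, so the expected precision is a central property of the design. The stated precision belongs to an unadjusted comparison, while the inferential analysis is adjusted. If baseline explains half the variance in change, the error bars in SD-of-change units are overstated by a factor of 1/√0.5 = 1.41.

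The unnamed denominator looks more serious. With R² = 0.5, one raw difference in HOOS points is 0.64 when divided by the SD of change and 0.90 when divided by the residual SD. If the next trial took one number for the other, a standard two-group formula would give about 40 per group or about 21. The stated bounds of 0.27 to 1.53, put through the same formula, give anything from about 217 to 8 per group. That would make the effect size look like a poor guide to the larger trial.

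**Working it through.** **Inputs.** From Sample size considerations: 20 completers per group, effect size 0.9, power 80%, 95% bounds 0.27 to 1.53, R² about 0.50. From Randomization: 1:1 allocation. Alpha is not stated for Aim 2; two-sided 0.05 is assumed, in line with the 95% bounds. One-sided 0.05 would give 87.5% power at 0.9, which does not match.

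**1. Reproduce the stated figures (no covariate, SD of change = 1).**
- Standard error of the difference = √(2/20) = 0.316.
- Power at 0.9: 79.2% (noncentral t, 38 df) or 81.2% (normal). Stated: 80%.
- Effect detectable with 80% power: 0.909 (t) or 0.886 (normal). Stated: 0.9.
- Half-width: 1.96 × 0.316 = 0.62 (normal) or 2.024 × 0.316 = 0.64 (t). The bounds around 0.9 are therefore 0.28 to 1.52 or 0.26 to 1.54. Stated: 0.27 to 1.53, which lies between them.

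The stated figures are right for an unadjusted comparison of 20 with 20.

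**2. The same design under the planned ANCOVA.** Residual SD = √(1 − R²) = √0.5 = 0.707 SD of change, with 37 df.

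| R² | 80% power at (SD of change) | 95% half-width |
|---|---|---|
| 0.30 | 0.76 | 0.54 |
| 0.40 | 0.70 | 0.50 |
| 0.50 | 0.64 | 0.45 |
| 0.60 | 0.58 | 0.41 |

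At R² = 0.50, power at 0.9 SD of change is 97.5%. A reader can get close by scaling the stated figures: 0.9 × 0.707 = 0.64 and 0.63 × 0.707 = 0.45.

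**3. The same ANCOVA in residual-SD units.** Detectable effect = 0.643/0.707 = 0.91; half-width = 0.453/0.707 = 0.64. These are essentially the stated figures, so the factor of 1.41 exists only in SD-of-change units.

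**4. The apparent twofold effect on the next trial** (80% power, two-sided 0.05, t-based).
- 0.90 with an unadjusted test: 21 per group. 0.64 with an unadjusted test: 40 per group.
- 0.64 SD of change analysed by ANCOVA with R² = 0.5: 0.64/0.707 = 0.905 residual SD, which needs 21 per group.
- 0.90 residual SD analysed by ANCOVA: 21 per group.

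The 40 arises only when an effect in SD-of-change units is paired with a test that discards the covariate. When effect size and analysis match, both denominators give 21.

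**5. The range of 217 to 8.** This uses the unadjusted bounds. With the adjusted half-width, the bounds around 0.9 are 0.90 ± 0.45 = 0.45 to 1.35. They give 79 to 10 per group with an unadjusted test, or 40 to 6 with ANCOVA. The range is still wide, as it is for any pilot of this size, and rewording the power sentence would not narrow it.

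**The case for a change.** The strongest case for a change is that saying precision will increase, without saying by how much, leaves the reader with the precision of an analysis that will not be used for inference. It also leaves an effect size with no stated denominator to be carried into a larger trial. The remedy is cheap: one sentence, a named SD, and a few summary statistics from data already collected. Being conservative for this pilot does not protect the next trial from a mixed-up denominator.

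Part of this stands. The adjusted figures are absent, the standardiser is unnamed, and supplying both would help. But the plan gives the R² needed for the conversion in the very next sentence, and its remark that the covariate raises power points to the SD of change as the design unit. An analyst reporting an ANCOVA will have the adjusted difference in HOOS points and the residual SD to hand. Nothing in the plan says that the next trial would pair an effect size with the wrong analysis, or that its sample size would rest on the pilot point estimate alone.

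Making the adjusted figure the headline has a cost too. The 50% is approximate and comes from preliminary work; the previous study described in the protocol randomised 35 people. An unadjusted floor with a note that adjustment helps is a fair choice when R² is this uncertain.

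Sizing the future trial on the minimum important changes of 6 (ADL) and 9 (Symptoms) lies outside this protocol. The primary outcome section itself says that such values are not established for non-surgical management and takes these from arthroscopic surgery patients.

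**Conclusion.** The concern does not call for a change. The stated 0.9 and 0.27 to 1.53 are arithmetically correct for an unadjusted comparison, and the plan openly presents them as figures that the covariate will improve. Under the planned ANCOVA the design does better: about 0.64 SD of change at 80% power and a half-width of about 0.45 if R² is 0.5, with ranges of 0.76 to 0.58 and 0.54 to 0.41 for R² from 0.3 to 0.6. Any error is in the safe direction, and the sample size, analysis and conclusions stay as they are.

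This rests on two-sided alpha of 0.05, 20 completers per group, and reading the stated effect size in SD-of-change units. In residual-SD units there is almost no gap to explain. What is left is a reporting detail that analysts would ordinarily supply: which SD standardises the effect, and the adjusted difference in points with its residual SD.

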Aim 2: Post-treatment improvement in outcomes (Fig. 4): Informed consent will be obtained prior to testing. Participants will complete self-report questionnaires and participate in movement pattern assessment. Participants will then be randomized into 1 of 2 treatment groups, movement pattern training (MPT) or standard rehabilitation (Control). Both groups will participate in 10 supervised sessions and perform a home program

within a 12 week time frame. At 13 weeks after enrollment, participants will return for testing to assess post-treatment improvements in primary and secondary outcomes.

Specific Procedures (Aims 1 and 2)

Primary outcome – Function: At pre-treatment and post-treatment testing, participants will complete the Hip disability and Osteoarthritis Outcome Score (HOOS),⁴² a reliable and valid³⁴ hip-specific, patient reported outcome measure. Basic demographic, medical history and medication use will also be collected. (Appendix 1). All questionnaire responses will be collected and managed using Research Electronic Data Capture (REDCap, See *Facilities and Other Resources*) system hosted at Washington University. We will use the tailored design method of survey procedures, used in our previous study, to motivate participants to respond.¹²

Minimum important change (MIC) for HOOS subscales has not been established for patients undergoing non-surgical management for PAHD. Using values established for people who have undergone arthroscopic surgery,³⁴ the MIC values for HOOS subscales of ADL and Symptoms are 6 and 9 respectively. In our **preliminary work**, statistically significant differences exceeding MIC were found in HOOS ADL and Symptoms, with those participating in MPT demonstrating greater improvement at follow up compared to those in the wait-list group (Fig. 2).

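### Must the plan single out one HOOS score as primary before its 0.9 effect size and 80% power have a meaning?

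*Combined protocol and SAP*

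**What the plan says.** Under Specific Procedures, the entry for the main outcome begins "Primary outcome – Function: At pre-treatment and post-treatment testing, participants will complete the Hip disability and Osteoarthritis Outcome Score (HOOS". The heading is singular and gives an instrument, not a score. The same entry says "the MIC values for HOOS subscales of ADL and Symptoms are 6 and 9 respectively", values borrowed from arthroscopic surgery patients because none exist for non-surgical care. It adds that in the preliminary work "statistically significant differences exceeding MIC were found in HOOS ADL and Symptoms". Randomization is stratified by HOOS Symptoms quartile, among other factors. Post-treatment assessment plans to "assess change in functional ability (HOOS) and movement patterns".

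Sample size considerations states that, with at least 20 completers per group, "the study will have 80% power to detect large effect sizes of 0.9 or above", with 95% bounds of 0.27 to 1.53. It then says "preliminary data for the primary outcomes indicate that approximately 50% of the variance in change is explained by the pre-treatment value". Statistical Analysis specifies an ANCOVA in which "change is the dependent variable and the pre-treatment value is the covariate". Significance and future directions says "effect size estimates will guide the future, large RCT". No section calls a particular HOOS score primary.

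**The concern.** A singular heading and a later plural do not agree on how many primary outcomes there are, and the HOOS yields several scores. Three things could depend on the answer.

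- **The power statement.** It is a one-comparison figure. If two scores were co-primary and each had to be protected, it would not describe the design.
- **Clinical reading of 0.9.** The two subscales have different minimum important changes (6 and 9 points), so the same standardized effect could lie on different sides of the benchmark.
- **Planning of the next trial.** With no lead score, the larger of two estimates could be carried forward, and that value would be biased upward.

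In a confirmatory trial, any of these would justify asking for a named score before analysis.

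**Working it through.** **1. Reproduce the stated power.** Inputs from Sample size considerations: 20 per group, effect 0.9. The significance level is not written; two-sided 5% is assumed from the 95% bounds.

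- SE of a standardized difference = √(2/20) = 0.316.
- Normal formula: 0.9/0.316 = 2.846; 2.846 − 1.96 = 0.886; power = 0.812.
- Noncentral t, 38 df: power = 0.792.
- Bounds: 0.9 ± 1.96 × 0.316 = 0.28 to 1.52; with the t quantile 2.024, 0.26 to 1.54. The stated 0.27 to 1.53 lies between.

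A one-sided test gives 0.885 or 0.875 and does not match. The stated figure is therefore a plain two-sample calculation in SD units, without the covariate. No property of a particular HOOS score enters it.

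**2. Suppose the plural means two co-primary scores.** Testing each at 5% gives a familywise error of at most 1 − 0.95² = 0.0975 (independence; lower for positively correlated scores). At 2.5% each, power at 0.9 falls to 0.727 (normal) or 0.695 (t), and the effect detectable at 80% power rises from 0.91 to 1.01 (t).

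These figures omit the covariate. If the pre-treatment value explains half the variance in change, as the plan reports, the residual SD is √0.5 = 0.707 of the unadjusted SD. Ignoring the one degree of freedom spent on it, the detectable effect is:

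- one score: 0.9 × 0.707 = 0.64 SD;
- two scores at 2.5% each: 1.01 × 0.707 = 0.71 SD.

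Both are below 0.9, so the quoted figure is cautious on either reading.

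**3. Does 0.9 SD conflict with the minimum important changes?** The documents give no SD of change, so the question has no answer from the plan for either score. An effect of 0.9 SD equals the benchmark when the SD is 6/0.9 = 6.7 points (ADL) or 9/0.9 = 10.0 points (Symptoms). With the covariate these become 6/0.636 = 9.4 and 9/0.636 = 14.1. The two scores give different answers only if they share an SD and it falls in the window 6.7–10.0 (unadjusted) or 9.4–14.1 (adjusted). Below the window both reach 80% power at the benchmark; above it neither does. The plan does not tie 0.9 to either benchmark.

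**4. Size of a selection effect.** Assumptions, none in the documents: equal true effects on the two scores, correlation 0.5 to 0.8, and the larger estimate carried forward. The upward bias is half of SE × √(2(1 − ρ)) × √(2/π).

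| | SE | ρ = 0.5 | ρ = 0.8 |
|---|---|---|---|
| Unadjusted | 0.316 | 0.126 | 0.080 |
| ANCOVA | 0.224 | 0.089 | 0.056 |

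The plan's half-width is (1.53 − 0.27)/2 = 0.63, or 0.63 × 0.707 = 0.45 with the covariate. The bias is thus between 0.080/0.63 = 13% and 0.126/0.63 = 20% of the half-width unadjusted, with the same percentages after adjustment.

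**The case for a change.** The strongest case for a change is that estimation still needs a named quantity, that the future trial will use these estimates, that the plan does include between-group inference, and that two sentences written before analysis would remove any suspicion of choosing afterwards. The singular and the plural do differ, and movement pattern is labelled secondary, so the plural has no obvious referent other than the HOOS scores. That much stands: no section of the available text designates a score.

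The rest carries less weight. A single domain measured by an instrument with subscales is often called primary outcomes without contradiction, and ADL and Symptoms, named directly under the primary heading, are the likely pair. The ANCOVA sentence describes a method that can be applied to each outcome in turn; it does not require a single lead score. The plan speaks of effect size estimates in the plural, so the idea of one planning value is brought in by the reader, and nothing in the plan says that the larger estimate will be taken. The benchmark comparison needs an SD the plan does not give and uses values that the plan itself says are not established for these patients. Finally, the aims page, Appendix 1 and Fig. 2 are not in the available text, so a designation there cannot be ruled out.

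**Conclusion.** The concern does not call for a change. The available text leaves open which HOOS score or scores are primary, but no stated rule or figure is wrong as a result. The 80% power at 0.9 with 20 per group is right for any one continuous score, and the ANCOVA estimate with 95% bounds is valid for each score analysed. Because the second aim is expressly not definitive, no success claim depends on the choice. An analyst can sensibly run the same model on ADL and Symptoms and report both estimates with their bounds, which leaves planners of the next trial with both values in view.

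Naming a score would alter no calculation or analysis method. The possible selection bias, 0.06 to 0.13 SD, rests on assumed correlations and a selection step the plan does not contain, and is at most a fifth of the half-width of the interval. This conclusion rests on the two-sided 5% level inferred from the stated bounds, on the plan's approximate 50% for the variance explained, and on the trial keeping to estimation. A confirmatory claim on one chosen subscale would be a different matter.

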Timeline: We have developed a Manual of Procedures to facilitate consistency in participant recruitment, protocol implementation and data collection across sites. We are developing training modules to optimize the treatment providers' adherence to study protocol. The study planning phase will include a pretrial meeting of the Steering Committee and onsite training of study personnel. Methods for the proposed study, described below, were optimized in the previous study, therefore we will initiate participant recruitment within one month of study start. Recruitment will proceed for 17 months (months 2-18) with the last follow-up being completed by month 21. The last 3 months will be used for data analysis and study close-out.

Preliminary studies supporting the approach

Aim 1: Participant adherence: Based on the previous study (K23), we are confident we will meet recruitment and retention goals of the project. In the study, we randomized 35 people with PAHD into an immediate treatment group (n=18) or a wait-list control group (n=17). The treatment group participated in 6 sessions of MPT. Overall retention rate was 91%; 2 in the treatment group and 1 in the wait-list group did not return after baseline testing. Treatment adherence was high; 15 of 16 who participated in treatment attended all supervised sessions and 1 attended 5 of 6 sessions. Additionally, 89% of those in the treatment group reported

completing their home program at least once per day. Using methods optimized in the previous study, we anticipate similar adherence in the proposed study.

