Secondary outcome – Movement pattern: We will use a digital camera to acquire 2D hip motion while participants complete tasks of varying difficulty: step down, single leg squat, drop vertical jump. Markers will be placed on anatomical landmarks of the pelvis and thigh to assist with hip angle measurement. Previously published procedures²⁵ for camera placement and participant positioning will be used to optimize between-site data collection and reduce the effect of projection angles on the 2D measures. Participants will practice each movement prior to testing. We will then collect 3 trials of each movement. Commercially available software will be used to measure peak hip adduction motion. All measurements will be completed by trained personnel at Washington University, who will be blinded to treatment group.

In our **preliminary work**, we used 3D kinematic methods to quantify hip motion during the single leg squat. For the current study, we chose to use a 2D method that can be easily replicated with simple equipment in the clinical setting. To assess our ability to predict 3D peak hip adduction angle using our proposed 2D method, we used digital videos synchronized to the 3D kinematic data collection. Using data from 12 randomly selected participants, we found the correlation between 2D and 3D peak hip adduction to be high ($r = 0.85$, $P < 0.001$). Test-retest reliability of our 2D method is excellent ($ICC_{3,3} = 0.996$); standard error of measurement of 0.47° .

Randomization: Participants will be randomized to 1 of 2 treatment groups in a 1:1 ratio stratified by sex and HOOS Symptoms quartile (as determined from the preliminary data) within each site. Within each stratum, participants will be allocated using a variable block size so that the desired allocation ratio will be maintained at intervals throughout the recruitment process. Randomization sequences will be generated a priori using a formal probability model and will be elicited from the data capture system. Given the nature of the intervention, it is not possible to blind the treatment providers or participants to treatment assignment. Study personnel performing the assessments or the movement pattern measurements will be blinded to group assignment.

Treatment: Treatment for both groups will include 10 supervised sessions over 12 weeks. After randomization,

[figure not shown]

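### Aim 1 compares adherence and retention between groups and sites by a Wilcoxon p-value only, with no estimate or bounds for the difference

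*Combined protocol and SAP*

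**What the plan says.** The Statistical Analysis section opens with the statement that "The primary data analyses for Aim 1 will be descriptive". It then deals with the feasibility rates in two steps. First, "Adherence, retention, and fidelity rates will be categorized using the specified thresholds and reported with 95% CBs". Second, "Uncategorized rates will be compared between sites and groups by Wilcoxon's test". No estimate or interval for a difference between groups or sites is described, and no alpha, power or target difference is given for the test.

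The Sample size considerations section gives precision for single rates only. "With a sample size of 46 (23/group"), the bounds for overall adherence and retention "will be between 78% and 96%, meaning that estimates will be within 9% of the true rate", and rates within a site or group are said to be within 13%. The stated condition is: "These calculations assume that the observed rates will be at least 90"%. The only power figure in that section belongs to Aim 2.

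Under Preliminary studies, Aim 1, the previous study reports 91% retention and that "15 of 16 who participated in treatment attended all supervised sessions"; the remaining participant attended 5 of 6.

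**The concern.** The Significance and future directions section says that adherence information from this study will shape the large trial, and that modifications will be made first if needed. One thing the next trial must know is whether people adhere less to one treatment, or at one site, than the other. The question is open: the pilot's session attendance and home-program figures come from movement pattern training only, the standard rehabilitation arm asks for different work, and Pittsburgh is a new site.

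A rank-test p-value does not answer that question. It says nothing about how large the difference is or how large it could still be. With 23 per group, a p-value above 0.05 can sit beside a difference big enough to matter for dilution and losses in the definitive trial, and a reader given only the p-value could take it as reassurance.

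**Working it through.** **Inputs.** 46 participants and 23 per group (Sample size considerations); 1:1 allocation by treatment (Randomization); 10 supervised sessions (General Procedures, Aim 2). Assumed because not stated: two-sided alpha of 0.05, and 23 participants per site.

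**1. The plan's own figures.** The Wilson score interval at a rate of 0.90 reproduces them.
- n = 46: 78.0% to 95.8%, half-width 8.9 points (stated: 78% to 96%, within 9%).
- n = 23: 71.6% to 97.0%, half-width 12.7 points (stated: within 13%).

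These describe one rate at a time, not a difference.

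**2. Bounds for a difference in a yes/no rate, 23 v 23.** Newcombe's interval combines the two Wilson intervals (l1, u1) and (l2, u2), with d = p1 - p2:
- lower = d - √[(p1 - l1)² + (u2 - p2)²]
- upper = d + √[(u1 - p1)² + (p2 - l2)²]

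The Wilson limits for 21/23 (0.913) are 0.732 and 0.976. Those for 16/23 (0.696) are 0.491 and 0.844.
- 21/23 v 21/23: d = 0, and √(0.181² + 0.063²) = 0.192, so -19 to +19 points.
- 21/23 v 16/23: d = 0.217; lower = 0.217 - √(0.181² + 0.148²) = -0.017; upper = 0.217 + √(0.063² + 0.204²) = 0.431.

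| Observed | Difference (points) | 95% bounds | Rank-test p |
|---|---|---|---|
| 21 v 21 | 0 | -19 to 19 | 1.00 |
| 21 v 19 | 9 | -12 to 29 | 0.39 |
| 21 v 18 | 13 | -9 to 34 | 0.22 |
| 21 v 17 | 17 | -5 to 39 | 0.12 |
| 21 v 16 | 22 | -2 to 43 | 0.07 |

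Every row would be reported as not significant.

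**3. Power for a yes/no rate, 23 v 23.** By exact enumeration, the tie-corrected Wilcoxon test has power of 16% at 90% v 80%, 41% at 90% v 70%, and 69% at 90% v 60%.

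**4. Per-participant session attendance.** The documents give no distribution for attendance out of 10. Assumption: a given share attend all 10 sessions and the rest are spread evenly over 0 to 9, averaging 4.5 sessions (45%). Mean attendance is then share + (1 - share) × 0.45:
- 94% full attenders: 0.94 + 0.06 × 0.45 = 96.7%
- 83%: 0.83 + 0.17 × 0.45 = 90.7%
- 74%: 0.74 + 0.26 × 0.45 = 85.7%

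Simulated with 23 v 23, using a t-based interval for the difference in means:

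| Full attenders | True difference in mean (points) | Wilcoxon rejects | Median farther bound, non-significant results | Interval reaches 30 points, non-significant results |
|---|---|---|---|---|
| 94% v 94% | 0 | about 2% | 11 | about 0% |
| 94% v 83% | 6 | about 19% | 16 | about 1.5% |
| 94% v 74% | 11 | about 46% | 20 | about 6% |

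**The case against.** The strongest reply is that estimation is already the plan. Aim 1 is descriptive, rates carry 95% bounds, and precision is planned within site and within group, so a reader would probably see each arm's rate and its bounds beside the p-value. No section ties a go/no-go rule or a claim of equivalence to this test. That stands, and it limits the consequence: misreading is a risk, not a planned step. It does not fill the gap, because two separate intervals are not an interval for the difference.

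A reader might also infer that differences of 30 points generally stay open after a non-significant result. The calculations do not support this. With 21/23 in the better arm, 30 points is reached only when the observed gap is about 13 points or more. For mean attendance at the ceiling it is rarely or never reached. Nor is a true 30-point gap usually missed: power is 69% at 90% v 60% for a yes/no rate, and 94% or more for attendance means of 90% v 60% under assumed beta-binomial distributions.

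Another tempting reading is that ties at the ceiling invalidate the test. They do not: a tie-corrected Wilcoxon test remains valid, and rejecting about 2% of the time under no difference is conservative. The ceiling itself is documented only for session attendance, in one arm with 6 sessions, while retention was merely high. Nothing is given on the distribution of home-program logs or fidelity.

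Finally, the text does not say how yes/no retention would enter as an uncategorized rate. Treating it as a comparison of two proportions is an inference.

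**Conclusion.** The point holds in a limited form. The only stated between-group and between-site comparison for Aim 1 is a p-value, and at 23 v 23 a non-significant p-value cannot be read as similar adherence or retention. For a yes/no rate, equal observed rates of 21/23 leave about ±19 points open, and 21/23 v 16/23 leaves -2 to 43. For mean session attendance near the ceiling the farther bound is typically 11 to 20 points.

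The yes/no figures rest on 23 per comparison group (assumed for sites) and 95% bounds. The attendance figures also rest on an assumed distribution and would change with it. The single less-than-full attender in the pilot missed only one session, so the even spread over 0 to 9 may be pessimistic. This is a worthwhile, inexpensive improvement to a secondary comparison within a descriptive aim. It does not make the planned analysis wrong.

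**What to change.** In the Statistical Analysis section, replace the Wilcoxon sentence with:

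> Differences between groups and between sites in the proportion adherent and retained are reported with Newcombe 95% CBs, and in mean sessions attended and home-program days with bootstrap 95% CBs. Wilcoxon p-values are supporting only, and a non-significant result is not taken as evidence of no difference.

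The cost is one sentence and a few lines of analysis code; no new data are needed. The downside is that the report will show wide bounds, which is what a sample of this size can support.
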